H00013594
2018-03-15

Official Title: Does the use of Liposomal Bupivacaine Decrease Narcotic Requirements in Geriatric Hip Fractures? A Randomized, Double Blinded Control Trial

NCT Number: NCT03289858

Date of the Document: March 15, 2018

1. Title

Does the use of Liposomal Bupivacaine Decrease Narcotic Requirements in Geriatric Hip Fractures? A Randomized, Double Blinded Control Trial

2. IRB Review History

N/A

3. Objectives

Decreasing pain and narcotic requirements in the elderly population following hip fracture could be associated with improved outcomes and the prevention of complications. Our goal is to conduct a multi-center prospective randomized control trial to determine if liposomal bupivacaine is superior to standard of care by addressing the below separate but related aims:

1. **Determine the effectiveness of Exparel to reduce narcotic requirements and pain post operatively after hip fracture treatment.** Excess narcotic use in the elderly population is associated with a host of complications often magnified by polypharmacy, including in hospital delirium, increased length of stay, nausea, constipation, urinary retention, respiratory depression and others. Decreasing narcotic usage in this group of patients following hip fracture can possibly reduce such complications. Patients will receive standard of care medical treatment and be randomized to intra-operative Exparel vs. placebo injections. Opioid requirements, complications, pain score, and length of stay will be assessed in the post-operative period.

- **Hypothesis:** We hypothesize that total morphine requirements and pain scores will be decreased in this group following the administration of exparel in the geriatric hip fracture fracture population.

2. **Determine the effectiveness of Exparel to reduce delirium in post-operative hip fracture patients.** In hospital delirium in elderly patients is associated with poor outcomes, including prolonged length of stay, poor participation in rehabilitation, and falls. Use of a locally administered liposomal bupivacaine could decrease the need for additional medications for pain control in addition to decreased mental stress for patients in this unfamiliar situation, thus resulting in decreased episodes of delirium. We will assess delirium utilizing Confusion Assessment Method (CAM) scores in the post-operative period at regularly scheduled intervals and compare average scores between the treatment / standard of care group.

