- End stage renal disease as defined by patients requiring hemodialysis at least twice weekly
- Polytrauma, defined as:
 - Concurrent upper or lower extremity fracture, pelvis fracture, spine fracture, rib fractures, or facial fractures
 - Blunt chest or abdominal trauma resulting in diagnosed organ injury
 - Head trauma resulting in intracranial bleed or diagnosed concussion
- Allergy to amide-type local anesthetics
- Prisoners (unlikely to be accessible for follow-up)

6. Study-Wide Number of Subjects

This is a multi-center study being conducted in conjunction with the University of Kentucky. The total recruitment goal is 60 patients, with a goal enrollment of 30 patients at University of Massachusetts, and 30 patients at University of Kentucky.

Recent studies evaluating regional nerve blocks in hip fractures have shown an average morphine sulfate equivalent of 3.5 +/- 0.52 mg/d in the first 3 postoperative days²⁶. That same study showed a 33% reduction in morphine equivalents (3.5 mg/d vs 2.1 mg/d). Assuming a similar effect size, this study would require only 8 patients group to be powered to 80% with a significance level of 0.05. With a target recruitment goal of 50 patients, the study would be powered to detect differences as low as 0.42 mg/d (a 12% effect size). Assuming a 10-20% loss to follow-up, we aim to recruit a total of 60 patients studywide (i.e. 30 at each site).

7. Study-Wide Recruitment Methods

Recruitment methods will be the same at both University of Massachusetts and University of Kentucky. Refer to [24. Recruitment Methods](#) for details of recruitment methods at University of Massachusetts.

8. Study Timelines

- Duration of an individual subject's participation in the study

An individual subject's participation in the study begins at enrollment and ends after the 30 day post-op follow-up period.

- Duration anticipated to enroll all subjects

From recent internal data review, we treat between 250-300 hip fractures annually at UMMMC. We anticipate 10-25% of patients will be both eligible and willing to enroll in the study, so to enroll 30 patients should take 6-12 months.

- Estimated date for the investigators to complete this study (complete primary analyses)

Primary analysis should be completed once the final cohort of patients complete their 30 day study window, so we expect 13-14 months after initiation of enrollment.

9. Study Endpoints

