- **Primary Outcome Variables:** Total morphine equivalents in the post-operative period for 24, 48, and 72 hours, CAM score and average Pain Visual Analog Scale
- **Secondary Outcome Variables:** Length of stay, discharge disposition, timing and participation with inpatient physical therapy, complications and 30 day readmission.

10. Procedures Involved

- **Patient identification:** Patients will be identified on morning intake rounds by the trauma team and the research staff who are present daily to screen and enroll patients.
- **Screening/Enrollment:** The research staff will review the charts to identify patients meeting the inclusion/exclusion criteria. Patients will be approached for study participation and enrolled in the study prior to surgery. For potential participants, the research staff will interview the patients, confirm willingness to participate and inclusion/criteria.
 - We will utilize a Mini-COG (Screening for Cognitive Impairment in Older Adults)²⁷. A score of <4, which has been shown to have high sensitivity for dementia screening will define cognitive impairment and will preclude enrollment.
 - At time of enrollment, preoperative demographics will be recorded which will include age, sex, comorbidities, current use of anti-epileptic/anti-depressive medications for pain control, type of surgical approach, pre-ambulatory status and implant class.
 - After this review and screening, the patient will be given the opportunity to ask researchers questions about the study. It will be reiterated to all patients during preoperative discussions that their enrollment status in no way will affect their ability to get adequate post-operative pain control.
- **Randomization:** Randomization will be done through the research pharmacy. Participants will undergo block randomization (block size: 10) through a computer-generated algorithm.

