Research subjects will be identified, recruited and followed post-operatively as inpatients at the University Campus of UMass Memorial Medical Center (UMMMC). They will be followed post-discharge at the Ambulatory Care Center (ACC). Data analysis will primarily occur in locked, private offices at in one of two secure research offices located at the University Campus.

22. Resources Available

UMass Memorial is the largest health system in central Massachusetts. It consists of three separate campuses, Hahnemann, Memorial, and University campus. The Orthopedics Department has locations on all three campuses that each provide a dedicated research space, which contain computers with access to password-protected research drives.

The Principle Investigator (PI) will be responsible for overseeing the study and ensuring consistency throughout the project. The orthopedic PI will serve as the research coordinator and assist in data collection and analysis. Recruitment and consent will be performed by the PI or the research assistant. Each member of the research staff has passed the CITI exam on ethical conduct of research and have received training and supervision regarding patient confidentiality and study protocol. The PI will meet with all research staff periodically to review each role and ensure adequate training for the respective positions. Upon enrollment of each patient, the corresponding surgical team will be counseled concerning the details of the study and their role, prior to admitting the patient into the OR.

The hospital research pharmacy has already been approached about this study and a protocol is in place to ensure appropriate randomization, blinding, and treatment occurs for the study-related portion (injection of Exparel vs. placebo at the conclusion of the operation).

The PI and research assistant will be responsible for institutional /IRB communication as well as data review and assistance with follow-up patient coordination as needed. There are no anticipated adverse consequences associated with this study, however, the principal investigator and research assistant will both be available should any unexpected medical or psychological problems arise. The research subjects will be provided with appropriate contact information in the consent form and will be provided with the PIs contact information at the time of enrollment as well.

23. Prior Approvals

Not applicable

24. Recruitment Methods

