No formal external recruitment methods will be used for this study, as hip fracture patients are universally admitted to the hospital after injury while awaiting surgery. Patients will be identified, screened, and approached for enrollment in the study as noted above (see 8. Study Timeline). After review and screening, the patient will be given the opportunity to ask researchers questions about the study. It will be reiterated to all patients during preoperative discussions that their enrollment status in no way will affect their ability to get adequate post-operative pain control. There will be no financial compensation in return for participation in this study.

25. Local Number of Subjects

The local recruitment goal at University of Massachusetts is 25 patients (Refer to 6. Study-Wide Number of Subjects)

26. Confidentiality

As part of our design, researchers will have access to patients' names and phone numbers in order to collect the required data. Upon enrollment, each patient will also be assigned a unique identifier. All patient personal information will be stored in a master list that links the patient's identifying information to their medical record number, which will be maintained in a separate, locked file that only approved research personnel will have access to. During the data collection period, researchers will not directly use this master list and, instead, will draw upon information from a separate that contains only the patient's first name, phone number, and unique patient identifier

All paper data collection documents are kept in locked file cabinets within locked offices that are accessible only to the project investigators and staff. All online databases are password protected to guard against unauthorized access and only approved research personnel will be granted access.

27. Provisions to Protect the Privacy Interests of Subjects (HIPAA)

All eligible subjects will be identified by orthopedic trauma team and researchers during morning intake rounds. After this point, only approved research personnel will have access to patients' private health information. All research will be stored electronically on secure research drives or locked offices as described above.

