Patients will be given ample time to review the contents of the consent in private. The patient will be approached about the study as soon as they are identified to give them adequate time to review the study information prior to surgery. A researcher will then be available to answer all questions regarding the patient's participation in the study, including but not limited to all risks and benefits. The patient may refuse to participate at any time during the consenting process or over the course of the study.

31. Process to Document Consent in Writing

The consent will be documented in accordance with the guidelines detailed previously in the HRP-803 INVESTIGATOR GUIDANCE: Documentation of Informed Consent. The patient will receive a copy of this consent for their personal records during the enrollment process. This consent has been largely modeled after the Template Consent Document (HRP-502) and provides answers to many anticipated questions. Each signed consent will be stored in a locked cabinet in a secure research office that only approved study personnel are able to access.

32. Drugs or Devices

Exparel (liposomal bupivacaine) is FDA approved, with a labeled indication of "single-dose infiltration into the surgical site to produce postsurgical analgesia". As such, this study represents on-label use of the medication. Use of Exparel post-operatively in this patient population does not involve a novel route or dosage, and is not being used in a patient population that would increase the risks. Exparel is

routinely used during arthroplasty surgery at our healthcare system Memorial Hospital in a population with a similar (although not identical) age profile and medical comorbidity profile. Additionally, this medication was routinely used at other institutions that the PI has trained at in hip fracture patients without identified increased medical risks or complications.

We will maintain coordination with the research pharmacy to store, handle and administer the drug, in accordance with the study procedure. The IDS will be responsible for drug preparation and accountability. Refer to 8. Study Timelines for details on the study procedure. Placebo will consist of normal saline. Exparel is not a clear/transparent solution, so per discussion with the IDS, blinding will be performed by delivery of the medication in an opaque syringe.

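### One fixed block size of 10, stated in the protocol, makes late assignments in a block predictable if masking at injection fails

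*Protocol*

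**What the plan says.** - **Randomization (protocol section 10).** "Randomization will be done through the research pharmacy", by computer algorithm, and "Participants will undergo block randomization (block size: 10". No second size is given. Section 3 says that patients will "be randomized to intra-operative Exparel vs. placebo injections". Neither the allocation ratio nor whether blocks run within site is stated.
- **Numbers.** In section 6, "The total recruitment goal is 60 patients", 30 per site. In section 25, "The local recruitment goal at University of Massachusetts is 25 patients".
- **Recruitment.** Section 10: "Patients will be approached for study participation and enrolled in the study prior to surgery". Section 22: "Recruitment and consent will be performed by the PI or the research assistant".
- **Masking.** Section 32 states that "Exparel is not a clear/transparent solution", that the placebo is saline, and that an opaque syringe provides the blinding. Under Treatment in section 10, 60 cc is infiltrated into tissue at the end of surgery, and the medication record gets the same kind of entry for drug or placebo. Section 20 says that researchers and subjects are unaware of assignment. Section 13 allows unblinding for certain unexpected complications.
- **Who knows the block size.** Section 18 has all sites hold the current protocol. Nothing keeps the block size from those who recruit.
- **Analysis.** The SAP lists t-tests and chi-square or Fisher tests, with no adjustment for site or baseline variables.

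**The concern.** In a permuted block of known, fixed size, anyone who knows the earlier arms can work out the last ones. Three features make this worth checking here. The block size is in a document that the sites hold. The two fluids differ in appearance, and the documents do not say how fluid is masked once it leaves the syringe. Nothing bars a person present at an injection from recruiting later patients. Volume is also low: 30 patients per site in 6 to 12 months is 2.5 to 5 a month, so a running count could be kept.

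At stake is selective enrolment. A recruiter who foresees the next arm could approach, defer or pass over a patient accordingly. The resulting baseline imbalance would not be corrected by an unadjusted t-test.

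**Working it through.** The plan gives no predictability figure, so there is none to reproduce. The inputs are a block of 10 (section 10), 60 patients (section 6) and 1:1 allocation, which is **assumed**. Each block of 2m = 10 then holds m = 5 per arm.

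**1. Certain assignments, all earlier arms known.** Position k is certain when all five of one arm fall in the first k-1 places: P(k) = 2 x C(k-1,5) / C(10,5), with C(10,5) = 252.

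| Position | Calculation | P(certain) |
|---|---|---|
| 1-5 | - | 0% |
| 6 | 2 x 1/252 | 0.8% |
| 7 | 2 x 6/252 | 4.8% |
| 8 | 2 x 21/252 | 16.7% |
| 9 | 2 x 56/252 | 44.4% |
| 10 | 2 x 126/252 | 100% |

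The sum is 420/252 = 1.67 per block, which agrees with 2m/(m+1) = 10/6. Six blocks give 6 x 1.67 = 10 of 60, or 16.7%. If blocks run within site and a site stops at 25, the share is 2 x 1.67 / 25 = 13.3%, because the first five places of the third block are never certain.

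**2. Best guessing, all earlier arms known.** Always guessing the arm that is behind gives m + (4^m/C(2m,m) - 1)/2 = 5 + (1024/252 - 1)/2 = 6.53 correct per block, or 65.3%.

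**3. Partial knowledge.** This was simulated for a site of 30. The recruiter knows where each block starts and recognises each earlier arm with probability q.

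| q | Certain | Guess correct |
|---|---|---|
| 1 | 16.7% | 65% |
| 0.9 | 9.8% | 62.7% |
| 0.75 | 4.0% | 60.0% |
| 0.5 | 0.5% | 56.7% |
| 0.25 | 0.03% | 53.9% |
| 0 (masking intact) | 0% | 50% |

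If blocks span both sites, a recruiter who sees only local cases sees about half of each block, so the q = 0.5 row is roughly the most that person could reach.

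**4. Varied block sizes.** This was simulated for a site of 30. The guesser knows every earlier arm and the set of sizes, but not the size of each block. Ranges come from repeated runs.

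| Sizes | Certain | Guess correct |
|---|---|---|
| Fixed 10 | 16.7% | 65.3% |
| 4/6 | about 5.7% | 68.8% |
| 4/6/8 | 2.5% | 67.4% |
| 6/8/10 | 1.7-1.8% | 65.5-65.6% |
| 8/10/12 | 1.4-1.7% | 64.2-64.3% |

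Varying the size removes certainty but not informed guessing, and small blocks make guessing easier. The share of assignments predictable with more than 80% confidence moves less than the share that is certain: 17.2% for fixed 10, 13.9% for 6/8/10 and 11.3% for 8/10/12.

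**The case against.** The strongest reply is that the protocol already deals with the difference in appearance. The sentence that says the drug is not clear goes on to specify the opaque syringe. The pharmacy holds the randomization and prepares both solutions, the medication record does not separate the arms, and section 20 states that researchers are blinded. With masking intact, a known block size gives no foreknowledge at all. A block of 10 is also fairly large for a site of 30, and harder to guess than 4 or 6.

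All of that stands, and it makes the point conditional. It does not remove it. An opaque barrel hides fluid only while the fluid is inside, and the protocol describes no masking during infiltration. Section 13 also provides a route by which some past arms become known.

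A reader might infer that past assignments are visible at injection, that the principal investigator sees them, or that all staff know the block size. The documents support none of these. They do not say whether the principal investigator operates on or injects trial patients. Section 18 shows only that sites hold the protocol, and nothing shows when it became public.

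**Conclusion.** The concern holds as a conditional, low-severity design point. A fixed block size known to the sites becomes a weakness only if masking at injection fails or earlier arms are otherwise learned. The ceiling is 16.7% of assignments certain (10 of 60) and 65% correct guessing. That ceiling rests on 1:1 allocation, full blocks, and knowledge of every earlier arm in the block. With partial knowledge, or with blocks that span both sites, the figures are much lower.

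A reader might take 10 of 60 as the expected number of foreseen assignments, or conclude that enrolment will be selective. Neither follows: the figure is a worst case, and foreknowledge must also be acted on. The documents give no basis for estimating how often either would happen.

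**What to change.** Remove the block size from the protocol. Have the pharmacy hold an undisclosed list for each site with randomly varied block sizes that are not small, for example 6/8/10 or 8/10/12. Avoid 4/6, which would raise worst-case guessing to 68.8%. Apply the new list only to patients not yet assigned. In the worst case this cuts certain assignments to about 2% and leaves guessing at about 64-66%, so masking matters at least as much.

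The protocol should also state the allocation ratio and that lists are by site, describe how fluid is masked during infiltration, and say whether anyone present at an injection may recruit later patients.

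The cost is a new computer-generated list and a slightly larger possible final imbalance. An unfinished block of 12 can leave a site at most 6 apart. If both sites of 30 did so in the same direction, the split would be 36 to 24, and 4 x 36 x 24 / 60^2 = 0.96, a 4% loss of information in that extreme. If enrolment is complete, report the scheme, the screening logs and baseline balance instead.

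Including site in the analysis is a separate small improvement. It does not correct selection bias within a site.

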- **Treatment:** Surgical treatment will be performed according to the attending surgeon and is independent of the study. At the conclusion of surgery, they will receive a subcutaneous injection of either Exparel placebo. Patients will receive operative treatment of the hip fracture per the operating surgeon. At the conclusion of surgery, Exparel will be given in 20cc doses, diluted with 40cc of normal saline to make 60cc of total injection volume. The injection solution contains a total of 266mg free base bupivacaine (equivalent of 300 mg bupivacaine HCl). The research pharmacy will prepare the injection solution to contain either Exparel or placebo solution. In intra-capsular arthroplasty cases, the solution will be injected circumferentially into the capsule, surrounding musculature, and subcutaneous layer. In cases with extra-capsular fractures treated with sliding hip screws or cephalomedullary nails, the solution will be administered in the deep tissue and muscles around the fascial incisions as well as in the subcutaneous layer. At the time of medicine or placebo administration, the operating room circulating nurse will create a log entry for Exparel administration in the medication administration record (MAR). This is the section of the medical record where all medications must be recorded, and will be consulted prior to delivery of any other local anesthetic agents, which will serve to limit the additional exposures and minimize the risk of toxicity.
- **Post-operative inpatient care:** While admitted to the hospital, patients will receive medical care per routine, including a standardized post-operative pain control regimen. Post-operatively, all patients will receive a uniform pain control protocol consistent with the current standard of care. We have worked with our anesthesia team to create a consensus-driven protocol to ensure patients are

evaluated for pain and having pain treated in an appropriate and uniform manner. The written protocol is included at the conclusion of this document as Appendix A. We will collect the following data from inpatient hospitalization.

- As a part of the research study regiment, delirium will be assessed using the Confusion Assessment Method (CAM)²⁸, which will be administered 6 hours following surgery, post-operative day 1, 2 and 3 between 8AM-12PM, when a provider is called to the bedside to evaluate the patient for confusion, and also by nursing staff at each nursing shift (Q12).

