Appendix A: Post-operative Pain Control Protocol

- Preop management
- Intra-op
 - Spinal vs. GETA per anesthesia and orthopaedic surgeon discussion with patient
 - Exparel vs placebo at conclusion of case
- Post-op / floor:
 - Standard PACU / floor pain assessment protocol
 - No toradol
 - Standing Tylenol 650mg PO q6hrs
 - Pain > 4/10, one dose 2.5mg PO oxycodone
 - Pain > 8/10, one dose 5mg PO oxycodone
 - Breakthrough pain: additional oxycodone 5mg PO once
 - Rescue pain: Hydromorphone 0.1mg IV once

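### Anaesthesia type and any block or other local anaesthetic given before the study injection are not listed for collection or adjustment, which may cost precision on the opioid outcome

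*Protocol*

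**What the plan says.** - **Anaesthesia.** Protocol Appendix A leaves the choice open: "Spinal vs. GETA per anesthesia and orthopaedic surgeon discussion with patient". It lists no nerve block.
- **Other local anaesthetics.** Section 10 (Treatment) has the circulating nurse log the study injection in the medication administration record (MAR) when it is given, and describes the MAR as the place where every drug has to be entered. The MAR "will be consulted prior to delivery of any other local anesthetic agents", with the stated purpose of limiting further exposure and toxicity. Section 15 describes plain bupivacaine as routine around hip fracture surgery at the site.
- **Data items.** The baseline list in Section 10 (Screening/Enrollment) comprises age, sex, comorbidities, "current use of anti-epileptic/anti-depressive medications for pain control, type of surgical approach, pre-ambulatory status and implant class". The later Section 10 list of items taken from the medical record covers opioid totals, VAS, physical therapy, length of stay and disposition. Neither list includes anaesthesia type or a nerve block. Under Section 12, the second site passes on de-identified data about the endpoints.
- **Planning data.** Section 6 and the SAP take their figures from a nerve-block study: "average morphine sulfate equivalent of 3.5 +/- 0.52 mg/d in the first 3 postoperative days", then "That same study showed a 33% reduction in morphine equivalents (3.5 mg/d vs 2.1 mg/d". A similar effect is assumed for the study drug.
- **Analysis.** Section 10 randomises in blocks of 10 and names no stratification factor. The SAP uses Student's t-test for continuous outcomes and names no covariates.

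**The concern.** The trial is sized on the effect of a nerve block. On the plan's own evidence, a block can therefore move the primary outcome by as much as the effect the trial hopes to see from the study drug. Yet the plan does not ask whether a trial patient had a block before the injection, or which anaesthetic was used.

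The MAR check does not fill this gap. It begins with the log entry made at the end of surgery, so it cannot bear on anything given earlier, and its purpose is safety rather than comparability of the arms. If such exposures vary between patients, their effect goes into the error term of an unadjusted comparison. A trial with 25 to 30 patients per arm can also be unbalanced on them by chance. At stake is the claimed sensitivity to differences as small as 0.42 mg/d.

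There is a practical side too. An item that is not listed will probably be missing from the second site's transfer, and Section 12 has identifiers destroyed after the secondary analysis, which makes later retrieval hard.

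**Working it through.** **Inputs from the documents (Protocol Section 6; SAP)**
- Significance level 0.05 and power 80% ("powered to 80% with a significance level of 0.05"). Two-sided testing and 1:1 allocation are assumed, as neither is stated.
- Spread 0.52 mg/d, read as an SD. The text does not say whether it is an SD or a standard error.
- Block effect: 3.5 − 2.1 = 1.4 mg/d. This is 1.4 / 3.5 = 40%, not the stated 33%, which would be 0.33 × 3.5 = 1.155 mg/d. Both are carried through.
- 50 evaluable patients, 25 per arm.

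**Assumed, because the documents give no figure:** the share p of patients with a pre-injection block (10%, 30%, 50%), and a block effect that adds to the treatment effect.

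**Step 1: the plan's own figure.** For a two-sample t-test with 25 per arm (noncentral t), the detectable difference is 0.8087 × SD. With SD 0.52 this is 0.8087 × 0.52 = 0.42 mg/d, as stated.

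**Step 2: add the block variance.** Total SD = √(0.52² + p(1 − p) × b²), where b is the block effect. For p = 30% and b = 1.4: √(0.2704 + 0.21 × 1.96) = √0.682 = 0.826, and 0.8087 × 0.826 = 0.67 mg/d.

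| Share with a block (assumed) | SD, b = 1.4 | Detectable difference, b = 1.4 | Power for 0.42, b = 1.4 | Detectable difference, b = 1.155 |
|---|---|---|---|---|
| 0% | 0.52 | 0.42 | 80% | 0.42 |
| 10% | 0.67 | 0.54 | 59% | 0.51 |
| 30% | 0.83 | 0.67 | 42% | 0.60 |
| 50% | 0.87 | 0.71 | 39% | 0.63 |

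Under these assumptions, adjusting for a recorded block would bring the detectable difference back to about 0.42 mg/d.

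**Step 3: a larger underlying SD.** With SD 1.5 (assumed) and no blocks, the detectable difference is 0.8087 × 1.5 = 1.21 mg/d. With 30% blocked and b = 1.4, SD = √(2.25 + 0.4116) = 1.63 and the detectable difference is 1.32 mg/d, a loss of about 9%.

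**Step 4: power for the planning effect.** With SD 0.52 and b = 1.4, power for 1.4 mg/d stays above 99% at every share in the table. With SD 1.5 it is 90% without blocks and 84% with 30% blocked; most of that shortfall comes from the larger SD, not from the blocks.

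**Step 5: chance imbalance.** A shift of 0.42 mg/d from blocks alone needs a gap between arms of 0.42 / 1.4 = 30 percentage points. With 25 per arm and simple randomisation, the probability of a shift that large in either direction is about 0.1%, 2.0% and 3.3% at p = 10%, 30% and 50%.

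**Spinal versus general anaesthesia.** The planning data give no figure, so no size can be calculated.

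**The case against.** The strongest reply is that nothing is wrong with the planned test. Under blinded randomisation an unadjusted t-test is valid, its standard error already allows for chance imbalance, and adjustment is a matter of efficiency. That stands. It also answers a reader who infers systematic bias: the documents give no route by which pre-injection exposure would depend on the arm.

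Two other strong readings also fail. One is that these exposures are unrecorded. Section 10 requires all medications to be entered in the MAR, so the drugs used are in the source record; what is missing is a listed study variable. The other is that they are uncontrolled. The MAR check and the uniform post-operative regimen set some limit, though only from the study injection onward. The preoperative heading in Appendix A has no text in the available copy, and nothing can be built on that.

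It is also fair to say that no section shows any trial patient receiving a block. Blocks appear only as background and planning evidence, the shares above are assumed, and at 0% the block covariate is irrelevant. The type and duration of the blocks in the planning study are not described either, so carrying its effect over to any block is a further assumption.

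Lastly, the planning effect is 1.4 mg/d, and 0.42 mg/d is spare sensitivity. That stands as well, and it limits the consequence.

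**Conclusion.** The point holds as a gap in data collection and precision. Anaesthesia type and pre-injection block or other local anaesthetic are not listed for collection or analysis at either site, and the SAP has no adjusted model.

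If 10% to 50% of patients have a block, the detectable difference rises from 0.42 to between 0.54 and 0.71 mg/d with a 1.4 mg/d block effect, or to between 0.51 and 0.63 mg/d with the stated 33%. This rests on the assumed shares, on additive effects and on 0.52 being an SD. With a true SD of 1.5 the loss at 30% is only about 9%.

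A reader might infer that the 0.42 mg/d claim has definitely failed, or that imbalance in blocks could readily create or conceal the effect. The documents support neither: block use is unknown, and a shift of 0.42 mg/d from imbalance has a probability of about 3% at most in the cases examined. Nor may the 1.4 mg/d figure be applied to spinal versus general anaesthesia; the case for that covariate is only that the choice is discretionary. This is a worthwhile improvement, not a flaw that invalidates the primary comparison.

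**What to change.** 1. Add two items to the Section 10 data lists at both sites: anaesthesia type, and any nerve block or other local anaesthetic given before the study injection (yes/no). Name both in the data set that the second site shares under Section 12.
2. In the SAP, pre-specify a linear model for the opioid totals and average VAS with terms for arm, site, anaesthesia type and pre-injection block. State in advance that the block term is dropped if almost no patient has one.
3. Report blocks given after the injection by arm, and do not adjust for them, since they may be a consequence of treatment.

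This sets no rule on whether blocks are given. It costs two fields to extract from existing records, about three degrees of freedom, and software that fits a linear model; Section 12 currently plans the final analysis in Excel spreadsheets.
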